APPENDIX D. PERFORMANCE STATUS SCALES CONVERSION

COPYRIGHTED MATERIAL

APPENDIX E. GUIDANCE ON CONTRACEPTION: PARTS A, B, AND C

Acceptable methods for highly effective birth control

Subjects who can father children^a and who are sexually active with a pregnant or breastfeeding person must use the contraceptives in Option 1 or 2:

- Option 1: Male condom with spermicide and cervical cap
- Option 2: Male condom with spermicide and diaphragm

Subjects who are of childbearing potential^b or whose partners are of childbearing potential who are sexually active in a way that could lead to pregnancy may choose to use any TWO of the following methods:

- Hormonal methods of contraception (excluding progestin-only pills).
- Intrauterine device with failure rate <1%
- Tubal ligation
- Partner's vasectomy (at least 90 days from the date of surgery with a semen analysis documenting azoospermia)
- A barrier method (male or female condom with spermicide, cervical cap with spermicide, diaphragm with spermicide)^c

^a A subject who can father children is anyone born male who has testes and who has not undergone surgical sterilization (eg, vasectomy followed by a clinical test proving that the procedure was effective).

^b A subject of childbearing potential is defined as anyone born female who has experienced menarche and who has not undergone surgical sterilization (eg, hysterectomy, bilateral salpingectomy, bilateral oophorectomy) or has not completed menopause. Menopause is defined clinically as 12 months of amenorrhea in a person born female over age 45 in the absence of other biological, physiological, or pharmacological causes.

^c A barrier method should only be used with a highly effective birth control method that is not a barrier method. Barrier methods alone, including a double-barrier method, are not considered highly effective contraceptive measures (see unacceptable methods of contraception)

Unacceptable methods of contraception

- Abstinence (including periodic abstinence)
- No method
- Withdrawal
- Rhythm
- Any barrier method without spermicide
- Spermicide only
- Progesterone-only pills
- Barrier methods alone; including double-barrier methods

Tables adapted from "Recommendations related to contraception and pregnancy testing in clinical trials" advisory non-binding guidance represented at the Clinical Trials Facilitation Group meeting, Rome 2014.

APPENDIX F. GUIDANCE ON CONTRACEPTION: PART D

Acceptable methods for highly effective birth control

Subjects who can father children^a and who are sexually active with a pregnant or breastfeeding person must use a condom even if the subject is vasectomized (must be confirmed by two negative semen analyses).

Subjects who are of childbearing potential^b are sexually active in a way that could lead to pregnancy may choose to use any TWO of the following methods:

- Intrauterine devices (IUD) excluding progesterone T
- Hormonal methods of contraception (hormonal patches, injections, vaginal rings, implants, or birth control pills excluding progestin-only “mini pills”).
- Tubal ligation
- Partner’s vasectomy (must be confirmed by two negative semen analyses)
- Barrier methods (male condoms and female diaphragm or cervical cap)^c

Subjects who can father children^a and are sexually active with a person of childbearing potential^b in a way that could lead to pregnancy must consistently use 2 methods of birth control, one of which must be a latex or synthetic condom even if the subject is vasectomized (must be confirmed by two negative semen analyses) along with any one of the following methods:

- Intrauterine devices (IUD) excluding progesterone T
- Hormonal methods of contraception (hormonal patches, injections, vaginal rings, implants, or birth control pills excluding progestin-only “mini pills”)
- Tubal ligation

^a A subject who can father children is anyone born male who has testes and who has not undergone surgical sterilization (eg, vasectomy followed by a clinical test proving that the procedure was effective).

^b A subject of childbearing potential is defined as anyone born female who has experienced menarche and who has not undergone surgical sterilization (eg, hysterectomy, bilateral salpingectomy, bilateral oophorectomy) or has not completed menopause. Menopause is defined per the pomalidomide REMS program as 24 months of amenorrhea in a person born female over age 50 in the absence of other biological, physiological, or pharmacological causes.

^c A barrier method should only be used with a highly effective birth control method that is not a barrier method. Barrier methods alone, including a double-barrier method, are not considered highly effective contraceptive measures (see unacceptable methods of contraception)

[figure not shown]
Unacceptable methods of contraception

- Abstinence (including periodic abstinence)
- No method
- Withdrawal
- Intrauterine device Progesterone T
- Rhythm
- Female condom
- Cervical shield
- Spermicide only
- Progesterone-only pills
- Barrier methods alone; including double-barrier methods

Tables adapted from “Recommendations related to contraception and pregnancy testing in clinical trials” advisory non-binding guidance represented at the Clinical Trials Facilitation Group meeting, Rome 2014.

APPENDIX G. NEW YORK HEART ASSOCIATION CLASSIFICATION

COPYRIGHTED MATERIAL

Online source: http://www.heart.org/HEARTORG/Conditions/HeartFailure/AboutHeartFailure/Classes-of-Heart-Failure_UCM_306328_Article.jsp

APPENDIX H. PROHIBITED CONCOMINANT MEDICATIONS

CYP3A4	Strong Inhibitors ¹	boceprevir, clarithromycin, cobicistat, danoprevir and ritonavir, elvitegravir and ritonavir, grapefruit juice, idelalisib, indinavir and ritonavir, itraconazole, ketoconazole, lopinavir and ritonavir, nefazodone, nelfinavir, paritaprevir and ritonavir and (ombitasvir and/or dasabuvir), posaconazole, ritonavir, saquinavir and ritonavir, telaprevir, tipranavir and ritonavir, telithromycin, troleandomycin, voriconazole
	Moderate Inhibitors ²	aprepitant, ciprofloxacin, conivaptan, crizotinib, cyclosporine, diltiazem, dronedarone, erythromycin, fluconazole, fluvoxamine, imatinib, tofisopam, verapamil
	Strong Inducers ¹	apalutamide, carbamazepine, enzalutamide, mitotane, phenytoin, rifampin, St. John's wort
	Moderate Inducers ²	bosentan, efavirenz, etravirine, phenobarbital, primidone
P-gp	Inhibitors ¹	amiodarone, carvedilol, clarithromycin, dronedarone, itraconazole, lapatinib, lopinavir and ritonavir, propafenone, quinidine, ranolazine, ritonavir, saquinavir and ritonavir, telaprevir, tipranavir and ritonavir, verapamil
	Inducers ²	rifampin

1 Drug Development and Drug Interactions: Table of Substrates, Inhibitors and Inducers [online]. Available from: <https://www.fda.gov/drugs/drug-interactions-labeling/drug-development-and-drug-interactions-table-substrates-inhibitors-and-inducers>. Accessed Jan 07, 2021.

2 This information is based on or an extract from UW Drug Interaction Database (DIDB) Copyright University of Washington. Accessed: Jan 05, 2021.

APPENDIX I. MODIFICATION OF DIET IN RENAL DISEASE EQUATION

- The estimated GFR should be calculated using the MDRD equation as applicable, with serum creatinine (Scr) reported in mg/dL ([Levey 2006](#)).
- $GFR \text{ (mL/min/1.73 m}^2\text{)} = 175 \times (\text{Scr})^{-1.154} \times (\text{Age})^{-0.203} \times (0.742 \text{ if female}) \times (1.212 \text{ if African American})$

APPENDIX J. DEFINITION OF RESPONSE AND PROGRESSION CRITERIA (MODIFIED FROM IMWG)

Response Subcategory	Response Criteria ^a
Stringent Complete Response (sCR)	CR, as defined below, plus the following: Normal FLC ratio ^b and absence of clonal cells ^c in bone marrow by immunohistochemistry or immunofluorescence
Complete Response (CR) ^b	Negative immunofixation of serum and urine and disappearance of any soft tissue plasmacytomas, and <5% plasma cells in bone marrow.
Very Good Partial Response (VGPR) ^b	Serum and urine M-protein detectable by immunofixation but not on electrophoresis or ≥90% reduction in serum M-protein level plus urine M-protein level <100 mg per 24 hour.
Partial Response (PR)	≥50% reduction of serum M-protein and reduction in 24-hour urinary M-protein by ≥90% or to <200 mg per 24 hour. If serum and urine M-protein are unmeasurable, a ≥50% decrease in the difference between involved and uninvolved FLC levels is required in place of the M-protein criteria. In addition to the above criteria, if present at baseline, ≥50% reduction in the size of soft tissue plasmacytomas is also required
Minor (Minimal) Response (MR)	25 to 49% reduction of serum M-protein and reduction in 24-hour urine M-protein by 50 to 89%, which still exceeds 200 mg per 24 hours. In addition, if present at baseline, 25 to 49% reduction in the size of soft tissue plasmacytomas is also required. No increase in the size or number of lytic bone lesions (development of compression fracture does not exclude response).
Stable Disease (SD)	Not meeting criteria for CR, VGPR, PR, MR, or progression.
Progressive disease	Any of the following: 
 • Increase of 25% from lowest response value in any one or more of the following: 
 1. Serum M-component (absolute increase must be ≥0.5 g/dL)^d and/or 2. Urine M-component (absolute increase must be ≥200 mg per 24 hr) and/or 3. Only in subjects without measurable serum and urine M-protein levels: the difference between involved and uninvolved FLC levels (absolute increase must be >10 mg/dL) 4. Bone marrow plasma cell percentage (absolute % must be ≥10%) • Definite development of new bone lesions or soft tissue plasmacytomas or definite increase in the size of existing bone lesions or soft tissue plasmacytomas • Development of hypercalcemia (corrected serum calcium >11.5 mg/100 mL) that can be attributed solely to the plasma cell proliferative disorder

a All response categories require 2 consecutive assessments made at any time before the institution of any new therapy; all categories also require no known evidence of progressive or new bone lesions if radiographic studies were performed. Radiographic studies are not required to satisfy these response requirements. Bone marrow assessments need not be confirmed.

b Note clarification to IMWG criteria for coding CR and VGPR in subjects in whom the only measurable disease is by serum FLC levels: CR in such subjects is defined as a normal FLC ratio of 0.26 to 1.65 in addition to CR criteria listed above. VGPR in such subjects is defined as a >90% decrease in the difference between involved and uninvolved FLC levels.

c Presence or absence of clonal cells is based upon the κ/λ ratio. An abnormal κ/λ ratio by immunohistochemistry and/or immunofluorescence requires a minimum of 100 plasma cells for analysis. An abnormal ratio reflecting presence of an abnormal clone is κ/λ of >4:1 or <1:2.

d For progressive disease, serum M-component increase of ≥ 1 g/dL is sufficient to define progression if starting M-component is ≥5 g/dL

Note: for IgA and IgD myelomas, quantitative immunoglobulin measurements are preferred for disease assessments; the same percentage change applies as for serum M-spike

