9.2.1. Objective Response Rate

A subject is determined to have an OR if, based on the 2016 IMWG uniform response criteria, they achieve a sCR, CR, VGPR, or a PR. The ORR is defined as the proportion of subjects with an OR per investigator. Subjects whose disease response cannot be evaluated per the 2016 IMWG uniform response criteria will be scored as Not Evaluable for calculating the ORR. Subjects who do not have postbaseline response assessment, or the response is Not Evaluable per IMWG criteria will be counted as non-responders in calculation of ORR.

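### Appendix J sets no plasmacytoma condition for VGPR, so a subject can fail PR yet meet VGPR and count in ORR; this could inflate ORR, by an amount that is unknown and may be zero

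*Protocol*

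**What the plan says.** Appendix J is the only operational definition of response in the two documents. Its rows treat soft tissue plasmacytomas as follows.

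- CR requires "disappearance of any soft tissue plasmacytomas". sCR inherits this, because its row starts from CR and adds to it.
- VGPR requires M-protein that is seen on immunofixation but not on electrophoresis, or "≥90% reduction in serum M-protein level plus urine M-protein level <100 mg per 24 hour". Plasmacytomas are not mentioned.
- PR: "if present at baseline, ≥50% reduction in the size of soft tissue plasmacytomas is also required".
- MR: "if present at baseline, 25 to 49% reduction in the size of soft tissue plasmacytomas is also required".
- PD includes a new plasmacytoma or a "definite increase in the size of existing bone lesions or soft tissue plasmacytomas".

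Footnote a adds that "all categories also require no known evidence of progressive or new bone lesions if radiographic studies were performed", and then that "Radiographic studies are not required to satisfy these response requirements". Footnote b redefines VGPR for subjects measurable only by free light chains (FLC) as a fall of more than 90% in the involved-minus-uninvolved difference, with nothing on plasmacytomas.

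Protocol 9.2.1 counts subjects as objective responders if "they achieve a sCR, CR, VGPR, or a PR". SAP 6.5.1.1 uses the same four categories, per investigator, with no further plasmacytoma rule. Protocol Section 6, Section 7.2 and Appendix A schedule plasmacytoma imaging where a plasmacytoma is known or suspected: at baseline, then every 4 cycles or to confirm PR or better.

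**The concern.** Response categories should be ordered, so that whoever meets a better category also meets the weaker ones. Here the order breaks at VGPR. Extramedullary disease that has not responded blocks CR, PR and MR but not the second-best depth of response.

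Best response, ORR and duration of response are secondary endpoints, and activity by dose level and schedule is one of the inputs to the recommended dose (protocol Table 1). VGPR or better is also the denominator for the MRD-negativity rate (protocol 9.2.7), and a first VGPR starts the clock for duration of response. Because response is assessed by the investigator, sites may settle the gap in different ways. Nothing in the exclusion criteria keeps subjects with plasmacytomas out.

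**Working it through.** **1. Is the condition supplied elsewhere?**

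| Source | Plasmacytoma condition | Applies to VGPR? |
|---|---|---|
| CR row (and sCR through CR) | must disappear | no |
| VGPR row | none | – |
| PR row | at least 50% reduction | only if VGPR is nested in PR, which is not stated |
| MR row | 25 to 49% reduction | no |
| PD row | new or definitely larger | an unchanged lesion is not PD |
| Footnote a, all categories | bone lesions only | does not cover soft tissue |
| Footnote b, FLC-only VGPR | none | – |

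Where the table means one category to build on another it says so: sCR on CR, and FLC-only CR on the listed CR criteria. It does not say that VGPR builds on PR.

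**2. Literal classification.** Take a subject with a baseline plasmacytoma and urine M-protein of 50 mg/24 h, and apply the rows as written:

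- VGPR if serum reduction ≥90% and urine <100 mg/24 h.
- PR if serum reduction ≥50%, urine <200 mg/24 h and plasmacytoma reduction ≥50%.
- MR needs a serum reduction of 25 to 49%, so it is not available here.
- Otherwise SD.

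| Serum reduction | Plasmacytoma reduction | As written | If VGPR also had to meet the PR plasmacytoma condition |
|---|---|---|---|
| 60% or 89% | 0, 30 or 49% | SD | SD |
| 60% or 89% | 50% | PR | PR |
| 90% or 95% | 0, 30 or 49% | VGPR | SD |
| 90% or 95% | 50% | VGPR | VGPR |

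The third line is the inversion. With the plasmacytoma unchanged, a serum fall of 89% is SD and a fall of 90% is VGPR. The last column is an illustration, not a claim about the source criteria.

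**3. Size in ORR.** The plan's own precision table (protocol 9.1, SAP 5.3) uses exact binomial limits at N=20. With B(q; a, b) the beta quantile, the limits for x responders of n are

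lower = B(0.025; x, n−x+1), upper = B(0.975; x+1, n−x).

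Reproducing the stated intervals:

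| x/20 | Computed | Stated |
|---|---|---|
| 6 (30%) | 11.9 to 54.3 | 12, 54 |
| 8 (40%) | 19.1 to 63.9 | 19, 64 |
| 10 (50%) | 27.2 to 72.8 | 27, 73 |
| 12 (60%) | 36.1 to 80.9 | 36, 81 |
| 14 (70%) | 45.7 to 88.1 | 46, 88 |

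All five agree. Each discordant subject moves ORR by 1/20 = 5 percentage points. From 6/20 = 30% (11.9% to 54.3%):

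- one more gives 7/20 = 35% (15.4% to 59.2%);
- two more give 8/20 = 40% (19.1% to 63.9%).

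The documents give no plasmacytoma prevalence. The range of 0 to 2 affected subjects per cohort is an assumption.

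**The case against.** The strongest reply is that Appendix J does not stand alone. Sections 7.2 and 9.2.1 name the 2016 IMWG criteria, which cannot be checked here. The VGPR row may reproduce that source, and in that case a threshold written in from outside would move the trial off its stated standard. This stands as a limit on the fix: the exact threshold has to be reconciled with the source. It does not remove the inconsistency. Appendix J presents itself as modified from IMWG, so a reader cannot tell whether the gap is deliberate, and SAP 6.5.1.4 cites the 2014 rather than the 2016 criteria for PFS.

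Second, imaging to confirm PR or better includes VGPR, which suggests that plasmacytoma status was meant to matter there, and an investigator could reasonably read VGPR as nested in PR. That is fair, and it makes this an ambiguity rather than proof of misclassification. The schedule still supplies no size criterion for VGPR.

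Third, a reader might infer that ORR is biased upward. The documents support only that it could be. An affected subject needs a baseline plasmacytoma, a VGPR-level M-protein or FLC response on two consecutive assessments, and shrinkage below 50% without definite increase. The number may be zero.

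Fourth, a reader might take footnote a to cancel plasmacytoma evaluation altogether. It does not: the CR, PR and MR rows keep their own conditions, and Section 6.6 requires evaluation at CR assessment for subjects with baseline plasmacytomas. The footnote is loosely worded, no more.

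Finally, the analyses are descriptive, and 1600 mg q2wk was already chosen as the expansion dose on the absence of DLTs and cumulative safety (protocol 3.2.1.1). This limits the consequence.

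**Conclusion.** The gap is real on the text. CR, PR and MR carry a plasmacytoma condition and VGPR carries none, so the better category can be reached where the weaker one is refused, and the subject counts in ORR. The scope is narrow: subjects with a baseline soft tissue plasmacytoma, a VGPR-level M-protein or FLC response, and less than 50% shrinkage without definite increase. Relative to a rule that nests VGPR in PR, the gap can only add responders, at 5 percentage points each in a cohort of 20. How many, if any, is unknown. No error rate or power figure is affected, because no hypothesis is tested.

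Two stronger conclusions are not supported: that ORR is in fact inflated, and that the PR threshold of 50% is established as the correct one for VGPR. The table supports a condition no weaker than the one for PR; the exact figure belongs to the cited criteria.

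**What to change.** - **VGPR row and footnote b:** state that, when a plasmacytoma is present at baseline, VGPR must also meet a plasmacytoma condition no weaker than the PR condition already in the table. Reconcile the exact threshold with the 2016 IMWG criteria.
- **Footnote a:** clarify that the sentence on radiographic studies does not waive evaluation of plasmacytomas known at baseline, in line with Section 6.
- **Analysis:** apply the corrected definition through the investigator's response assessment. ORR is per investigator in both documents, so a SAP rule that overrides the investigator would change the endpoint. Use the plasmacytoma evaluations that SAP 6.5 already lists to query discordant VGPRs, or to run a sensitivity ORR. Any sensitivity analysis must say how a VGPR without a matching scan is handled, because imaging may not coincide with every response, and should first confirm that size change is recorded.

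**Cost.** A few sentences in Appendix J and no new scheduled assessments. ORR may be slightly lower. A subject with a deep M-protein response but an insufficiently reduced plasmacytoma would be classed as SD, as already happens at PR-level M-protein reductions. SAP Section 8 already speaks of the final study report analysis in the past tense. If it is too late to amend the definition, the query or the sensitivity ORR is still available and should be described in that report.

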APPENDIX L. DOCUMENT HISTORY

Version	Date
Original	26-Mar-2018
Amendment 1	17-May-2018
Amendment 2	14-Feb-2019
Amendment 3	27-Feb-2020
Amendment 4	13-May-2020
Amendment 5	04-Mar-2021
Amendment 6	22-Mar-2021
Amendment 7	06-Aug-2021
Amendment 8	31-Mar-2022
Amendment 9	03-Jun-2022

Summary of Changes in Amendment 1

Section(s)	Change	Rationale
3.1.1 Table 2	
Revised the mTPI methodology to stipulate the following: Using a target DLT rate of 25% with a 5% margin, the 3 intervals will be (0, 20%), (20%, 30%), and (30%, 100%), and the corresponding dosing decision rules would be:
 
Escalate if current DLT rate is most likely <20%
 
Continue if current DLT rate is most likely between 20% and 30%
 
De-escalate if current DLT rate is likely >30%
 
The dose-finding spreadsheet was revised based to reflect the target DLT rate of 25% with a 5% margin
	To reflect that a target DLT rate 25% with a 5% margin will be used during dose-escalation
3.1.3 5.2.3	
Revised the DLT criteria to clarify that any treatment-related deaths will be considered DLTs.
 
In addition, AEs considered DLTs were revised to reflect the following:
 
 ○ Grade 4 neutropenia lasting more than 5 days ○ Thrombocytopenia \geq Grade 4, or Grade 3 thrombocytopenia with clinically significant bleeding ○ Any \geq Grade 4 infusion-related reactions (IRRs) or Grade 3 IRRs that do not resolve to \leq Grade 2 within 24 hours with infusion interruption, infusion rate reduction, and/or standard supportive measures. In the event of a Grade 3 IRR in \geq20% of subjects (ie, 2 or more in the first 10 subjects), all subsequent subjects will require premedication and/or modification of infusion approach per the recommendation of the SMC. For subjects receiving premedication, any \geq Grade 3 IRR will be considered a DLT. ○ Any Grade \geq3 electrolyte abnormality that does not resolve, with or without intervention, to \leq Grade 1 or the baseline grade within 72 hours 
Section 5.2.3 was revised to include additional follow-up for subjects with Grade 4 neutropenia or Grade 3 electrolyte abnormalities as follows:
 
During dose-escalation, subjects with Grade 4 neutropenia must have a follow-up CBC with differential obtained 5 days from the time of assessment for evaluation of DLT. In addition, subjects with Grade 3 electrolyte abnormalities must have a follow-up chemistry panel obtained 72 hours from the time of assessment for evaluation of DLT.
	To provide more conservative DLT criteria during dose-escalation
3.1.4	Revised the stopping criteria to indicate that the study will be halted if the rate of on-study toxic deaths unrelated to underlying disease occurring within 30 days of dose exceeds 10% (initially, 2 or more of the first 20 subjects)	To provide more conservative stopping criteria for on-study toxic deaths

Section(s)	Change	Rationale
5.2.2 6.4.1	
Revised the observation period for Cycle 1, Day 1 as follows: On Cycle 1, Day 1, subjects will be closely observed in the clinic for at least 6 hours after completion of study treatment administration during dose-escalation. Vital signs will be collected as described in Section 6.4. Additional monitoring for subsequent cycles will be considered upon review of safety data with the SMC. The observation period after completion of study treatment administration on Cycle 1, Day 1 may be reduced to 2 hours during dose expansion if the SMC determines that safety is adequate after review of data from the dose-escalation cohort.
 
In addition, vital sign monitoring time points of 240 minutes and 360 minutes were added to Schedule of Events for the Cycle 1, Day 1 visit for subjects in dose-escalation
	Extended observation after the Cycle 1, Day 1 infusion will be utilized during dose-escalation, and may be discontinued during dose expansion if supported by safety data
Table 4	
Revised the dose modifications for nonhematologic AEs and laboratory abnormalities as follows:
 
Grade 3: Withhold dose until toxicity is \leq Grade 1 or baseline^a, and then resume treatment at a lower dose level^b
 
Grade 4: Discontinue study treatment
	To revise the recommended dose modifications for SEA-BCMA-associated toxicity
Appendix C	
Revised the mTPI simulation report to reflect a target DLT rate of 25% with a 5% margin
 
Added Scenarios 5 and 6 to the simulation report
	To reflect the 25% target DLT rate and to expand the evaluation of the operating characteristics of the mTPI model

AE = adverse event; DLT = dose-limiting toxicity; IRR = infusion-related reaction; mTPI = modified toxicity probability interval; SMC = Safety Monitoring Committee

Summary of Changes in Amendment 2

Section(s)	Change	Rationale
Multiple	Revised to reflect that PK assessments are performed using serum samples only	Correction
3.1.1	Revised the required observation period between dosing of the first 2 subjects above Dose Level 1 from 72 hours to 24 hours	To reduce the time to dosing of the second subject at each dose level above Dose Level 1
7.6.1.2	
Revised the AE reporting requirements as follows:
 
Progression of the Underlying Malignancy-Cancer Since progression of underlying malignancy is being assessed as an efficacy variable, it should not be reported as an AE or SAE. The terms “Disease Progression”, “Progression of Disease” or “Malignant disease progression” and other similar terms should not be used to describe an AE or SAE. However, clinical symptoms of progression may be reported as AEs or SAEs if the symptom cannot be determined as exclusively due to progression of the underlying malignancy or does not fit the expected pattern of progression for the disease under study. In addition, complications from progression of the underlying malignancy should be reported as AEs or SAEs. Do not use the term “disease progression” alone when reporting AEs, including SAEs, because it is too nonspecific. Symptoms of disease progression that meet the criteria for an SAE must be reported. When possible, report the specific disease (clinical) manifestation of the progression (eg, “malignant pleural effusion”, “spinal bone metastases”, “lymphadenopathy”, “brain metastases”). Otherwise, it is acceptable to report the specific disease (eg, non-Hodgkin lymphoma) as an SAE.
	To clarify that disease progression should not be captured as an AE or SAE
7.6.1.2	Revised pregnancy monitoring requirements as follows: As part of the study, all pregnancies will be monitored for the full duration and all perinatal and neonatal outcomes should be reported.	To clarify that pregnancy monitoring is to be performed as part of the study
7.6.6	
Revised the requirement for electrocardiograms (ECGs) as follows:
 
Subjects will be monitored for changes in cardiac repolarization through assessment of ECGs conducted in triplicate at times outlined in Appendix A and Section 6. There is a 30-minute window to perform ECGs. Waiting periods between replicate ECGs are not required.
	To clarify that all ECG measurements are to be collected in triplicate
Appendix A	
Revised table to indicate that Day 15 ECG measurements are required during Cycle 1 only
 
Revised footnote A to clarify ECG collection requirements
	Clarification
Appendix B	Revised the time point associated with the Baseline/Screening visit from “predose” to “non-dosing”	Clarification

AE = adverse event; ECG = electrocardiogram; PK = pharmacokinetic; SAE = serious adverse event

Summary of Changes in Amendment 3

Section(s)	Change	Rationale
Title page	Updated phase of study from 1 to 1b	To reflect the amended study design
Synopsis, Sections 1.6.1, 2, 3.1.2, 3.1.8, 3.1.8.2, 3.3, 4.1, 6.3, 7.2, 9.1, 9.3.10, Appendix A, Appendix B	
Added Part B: Monotherapy Intensive Dosing Affected sections include
 
 • Rationale for intensive dosing schedule • Objectives • Study design • Safety monitoring • Method of assigning subjects to treatment groups • Inclusion criteria 
 ○ added criterion 4b. Part B and Part C: Subjects must have received at least 3 prior lines of antimyeloma therapy and must be refractory to at least 1 agent in each of the following classes: PI, IMiD, and an anti-CD38 antibody • Study activities • Response/Efficacy assessments • Determination of sample size • Interim analyses • Schedule of events • PK, biomarker, and biomarker sampling time points 	To evaluate an alternative SEA-BCMA monotherapy dosing schedule
Synopsis, Sections 1.6.2, 2, 3.1.3, 3.1.6, 3.1.8, 3.1.8.2, 3.3, 3.3.1.2, 4.1, 4.2, 4.4.1, 5.2.3, 5.3, 5.4, 6.4, 7.2, 7.3, 7.4, 9.1, 9.3.7, 9.3.10, Appendix A, Appendix B	
Added Part C: SEA-BCMA in combination with dexamethasone Affected sections include
 
 • Rationale for dexamethasone combination therapy • Objectives • Study design • Retreatment • Safety monitoring • Method of assigning subjects to treatment groups • Rationale for selection of combination therapy • Inclusion criteria 
 ○ added criterion 4b. Part B and Part C: Subjects must have received at least 3 prior lines of antimyeloma therapy and must be refractory to at least 1 agent in each of the following classes: PI, IMiD, and an anti-CD38 antibody • Exclusion criteria 
 ○ Added exclusion criterion 17. Part C only: Known intolerance to corticosteroids 	To evaluate the safety, tolerability, and efficacy of SEA-BCMA in combination with dexamethasone

Section(s)	Change	Rationale
	
 ○ Added exclusion criterion 18. Part C only: Any uncontrolled psychoses ● Discontinuation of study treatment ● Dose modifications ● Dexamethasone treatment 
 ○ Description, method of procurement, dose and administration, dose modifications, storage and handling, packaging and labeling, and preparation ● Required premedication and postmedication ● Study activities ● Response/Efficacy assessments ● Qualitative interviews ● Pharmacokinetic and immunogenicity assessments ● Determination of sample size ● Interim analyses ● Schedule of events ● PK, biomarker, and biomarker sampling time points 	
Section 1.1	
Updated with newly approved regimens for subjects with MM.
 
Removed the following sentence: SEA-BCMA in combination with an autologous T-cell product expressing an antibody-coupled T-cell receptor that recognizes antibodies, is currently being evaluated in a phase I study with MM subjects.
	Update with current information
Section 2, 9.2.6	Added exploratory endpoint to assess MRD in subjects with VGPR or better	To improve efficacy monitoring
Section 3.1.4	
Edited the following DLT:
 
 ● Any Grade ≥ 3 electrolyte asymptomatic laboratory abnormality that does not resolve, with or without intervention, to \leq Grade 1 or the baseline grade within 72 hours 	To improve safety monitoring
Section 3.1.7	Added section to allow treatment beyond progression under specified conditions.	To allow subjects receiving clinical benefit to be retreated
Section 3.3.1.1	Added rationale for selection of monotherapy expansion dose	Update with current information
Sections 5.2.3, 5.6.1	Updated dose modifications recommendations for SEA-BCMA monotherapy	To refine dose modification guidance; as IRRs have not yet been correlated with dose, and all IRRs that occurred during Cycle 1 Day 1 were successfully prevented by premedication at the next dose, dose reduction at the next dose can be considered but is not required

Section(s)	Change	Rationale
Section 7.7.3	Removed amylase and lipase from clinical laboratory tests	Streamline safety monitoring; no signal of pancreatic toxicity has been detected thus far on the phase 1 trial
Section 6.2, Appendix A, Appendix B	Removed q4wk SEA-BCMA dosing schedule	To remove unused dosing schedule
Sections 6.2, 6.3, 6.4, 6.9, 7.1, 7.7.3, Appendix A	Clarified that UPC calculation is urine protein to creatinine ratio and added units of mg/mg. For example, 
 • Urine protein to creatinine ratio (UPCR) calculation; 24-hour urine collection required if UPCR >2 mg/mg 	Clarification
Sections 6.6, 6.7, 6.8	Only subjects in Part A will have IHR and IHR follow-up visits	To specify that IHR visits are conducted for subjects in Part A only
Appendix H	Added definition of response and progression criteria modified from IMWG guidance	Clarification
Throughout protocol	Minor corrections and clarifications	Corrections and clarifications

BCMA = B-cell maturation antigen; CD38 = cluster of differentiation 38; DLT = dose-limiting toxicity; IHR = infusion/hypersensitivity reaction; IMiD = immunomodulatory drug; IMWG = International Myeloma Working Group; IRR = infusion-related reaction MM = multiple myeloma; MRD = minimal residual disease; PI = proteasome inhibitor; PK = pharmacokinetic; UPC = urine protein to creatinine; UPCR = urine protein to creatinine ratio; VGPR = very good partial response

Summary of Changes in Amendment 4

Section(s)	Change	Rationale
Section 6.2.3.1, Appendix A	Added text to specify that in Part A, ECGs will be conducted on Day 1 of Cycle 1, but not conducted on Day 1 of subsequent cycles.	To specify that in Part A, ECGs should not be conducted on Day 1 of Cycle 2 and subsequent cycles.

ECG = electrocardiogram

Summary of Changes in Amendment 5

Section(s)	Change	Rationale
Throughout	“Seattle Genetics” replaced with “Seagen” throughout	To reflect change in the company name
Synopsis, Sections 3.1.1, 3.2, and 5.2.3	Added criteria for intrasubject dose escalation.	To provide objective criteria for decisions about intrasubject dose escalation
Sections 3.1.2 and 3.1.3	If 2 or more DLTs occur in the first 6 subjects in any Part B or C cohort, the MTD will be considered exceeded.	To improve subject safety and enable a more accurate estimation of the MTD
Sections 3.1.3 and 3.3.1.2	Specified that in Part C Optional Cohort 2, SEA-BCMA will be administered at a dose of 800 mg during Cycles 1 and 2	To clearly specify the starting dose of SEA-BCMA dose in Part C Optional Cohort 2
Section 3.1.5	Study stopping criteria apply throughout the entire study	Clarification
Section 3.1.7	Removed section allowing treatment beyond progression	To require treatment discontinuation at the time of IMWG confirmed progressive disease
Section 5.2.3 and 5.6.1	Specified that recommended dose modifications are for toxicities regardless of relatedness to SEA-BCMA. Specified that after Grade 3 non-hematologic toxicities have recovered to baseline or \leq Grade 1, SEA-BCMA may be resumed at 50% of the previous dose.	To improve subject safety

Summary of Changes in Amendment 6

Section(s)	Change	Rationale
Protocol Synopsis	Added criterion for Part D to Study Population. Added Number of Planned Subjects for Part D. Added Part D Study Design. Added pomalidomide to Combination Products. Changes Statistical Methods to include 30 to 70% ORR (previously 30 to 50%).	To delineate the differences between Part D criterion, patient population, response benchmarks, and treatment from those for Parts A, B, and C.
1.1	Added information on the use of pomalidomide/dexamethasone in combination with monoclonal antibodies to treat multiple myeloma.	Justification of this combination with SEA-BCMA.
1.6	Added information on the favorable safety profile and preliminary evidence of clinical activity based on data from Part A.	Justification for the investigation of SEA-BCMA in combination with approved SOC agents.
1.3.2.2	Added rationale for pomalidomide and dexamethasone combination therapy.	To describe the enhancement of natural killer cell expansion and its potentiation of ADCC.
3.1	Added Study Design Schema image.	To visually clarify and summarize the 4 parts of the study design.
3.1.3	Added Part D to Combination Therapy Cohorts.	NA
3.3.6	Changed Retreatment criterion from a partial PR or better to clinical benefit (defined as stabilization or improvement of disease-related symptoms as assessed by the investigator).	To allow for consideration of retreatment in subjects receiving clinical benefit.
4.1	Added Part D to Inclusion Criteria. Added more stringent guidance for subjects of childbearing potential.	To delineate between criterion for Part D and those for Parts A, and B/C.
4.2	Added exclusion criterion specific to Part D.	To capture risks specific to pomalidomide treatment.
4.3	Added washout period guidance for females treated with FSH.	Improve subject safety
4.3.1	Added information specific to Part D for women of childbearing potential.	To delineate between criterion for Part D and those for Parts A, and B/C.
4.4.1	Added Discontinuation of Study Treatment information specific to Part D.	Information related to new Part D cohort.
5.4	Added pomalidomide section to Treatments.	Information related to new part D cohort.
5.6	Added required premedication regimen	Improve subject safety
5.7.1	Changes to Required Concomitant Therapy.	Emerging safety data as well as the requirement of thromboembolic prophylaxis with pomalidomide.
5.7.3	Added Part D to Prohibited Concomitant Therapy.	Information related to new Part D cohort.
6.2.3, 6.4.3	Added requirement that premedication be delivered approximately 45 to 90 minutes prior to the infusion of SEA-BCMA.	Improve subject safety

Section(s)	Change	Rationale
6.4.3.1	Changed UPCR calculation to spot urine test.	Clarification
6.5	Added Part D Study Activities.	Information related to new Part D cohort.
9.1	Assumption for Determination of Sample Size changed from ORR between 30 and 50% to between 30 and 70%.	Upper range of response increased due to addition of Part D combination therapy in an earlier line.
Appendix A	Premedication added to Schedule of Event tables for Parts B and C. Schedule of events table added for Part D.	Improve subject safety and information related to new Part D cohort.
Appendix B	PK, ATA, and Biomarker Sampling Timepoints added for Part D.	Information related to new Part D cohort.
Appendix F	Contraceptive guidance specific to Part D added.	Align with guidance required for pomalidomide.

Summary of Changes in Amendment 7

Section(s)	Change	Rationale
Global	Changed the term “patient” to “subject” when referring to a person who is involved in a clinical study	Modification to style guide
Global	Changed the phrase “approval of the SMC” to “recommendation of the SMC”	Accuracy of terminology
Synopsis	Clarified patient run-in language for Part C Optional Cohort 2	Clarification
Synopsis, 1.6.2.4, 3.1, 3.3.1.2, 4, 5.5, 5.7, 6.1, 9.1, 9.3 1.2, 1.6.2.3	Added new cohort: SEA-BCMA in combination with nirogacestat and dexamethasone (Part E)	New cohort
Synopsis, 3.1.3, 3.3.1.2, 6.5.3	Added new cohort: intensive dosing of SEA-BCMA in combination with pomalidomide and dexamethasone (Part D)	New cohort
7.7	Added adverse events of special interest to Reporting Periods Added investigator causality assessment to Serious Adverse Events Require Immediate Reporting New section on Adverse Events of Special Interest	To improve subject safety
Appendix A Appendix B	Schedule of Events and PK/ATA/Biomarker Sampling Tables added for Part D Cohort 2 and Part E	Information related to new cohorts
